4.9 Administration arrangements post recruitment (if applicable)

The centre research team should:

- File a copy of the consent form in the hospital/clinic notes along with information about the
- Enter trial data regarding the participant into the bespoke trial website.
- Maintain trial documentation at the centre.
- Return a copy of any signed paper consent form to the Trial Office.

PEPPY protocol version 3.0 26/02/2025 **ISRCTN: xxxxxx** Page 18 of 51

5. TRIAL INTERVENTION

The intervention being evaluated is a combination of treatments that are already provided (usually separately but more recently in combination) within the NHS. Development of the intervention protocol has been undertaken by our multidisciplinary team in consultation with PPI collaborators and professional bodies, mindful of Equality, Diversity and Inclusion (EDI) considerations. Centre staff involved in the research will receive training in delivery of the trial and the intervention protocols at a Site Initiation Visit (SIV).

5.1 Supervised PFMT plus vaginal pessary

The intervention being evaluated is an evidence-based supervised PFMT programme [5]: 16 weeks duration (5 appointments, with a minimum of 3 face-to-face), with the addition of a vaginal pessary being fitted. Women will receive an individualised PFMT programme which will be progressed at each appointment. At the first appointment an explanation of types of prolapse, anatomy and function of pelvic floor muscles will be given using diagrams and a model pelvis. An internal assessment of the pelvic floor muscles will be carried out to confirm a correct exercise technique and assess pelvic floor muscle strength and function (using the PERFECT Scheme) [19] and prolapse severity (a minimisation variable) will be recorded (POP-Q System: stage 0/1, stage 2, stage 3/4 - this is a simple version of the POP-Q staging [20]). An individualised home exercise programme will be prescribed based on examination findings. Women will be encouraged to progress exercises, with the aim of achieving ten times 10second maximum holds and up to 50 fast contractions three times per day. Exercises undertaken will be recorded by participants in a diary. Women will also be taught how to precontract the pelvic floor muscles against increases in intra-abdominal pressure (the Knack exercise) and be encouraged to use this technique daily. The home exercise programme will be modified at appointments on the basis of examination findings and diary recordings. Use of electromyography biofeedback, pressure biofeedback, and electrical stimulation as part of the PFMT programme will not be permitted. Such adjuncts may not be suitable for participants using a pessary in the PFMT and Pessary group, therefore will not be used in either trial group. Supervised PFMT will be delivered by a clinician (usually a specialist physiotherapist or nurse, depending on the service model at each centre) with formal training in pelvic floor rehabilitation.

[figure not shown]
A vaginal pessary will be fitted after the participant has completed the baseline questionnaire and been randomised (usually both will occur at the baseline/first PFMT appointment), in accordance with usual practice at the participating centre. There will be no restriction on pessary type, and women may be offered to self-manage their pessary if this option is available at their centre [21]. The type and size of pessary a woman uses will be recorded and reported. Pessary care will be delivered by a clinician (usually a gynaecologist, nurse or physiotherapist, depending on the service model at each centre) with specialist training in fitting and managing vaginal pessaries. Participants will be asked to use the pessary for at least 16 weeks (during the period of supervised PFMT) but can continue to use it if desired. Pessary review appointments will be offered to participants with the frequency dependent on whether they are self-managing or not. Participants who self-manage their pessary (who can remove the pessary themselves) will be asked to remove the pessary and those who do not self-manage will be asked to come to clinic to have the pessary removed 2 weeks before they receive their 6 and 12 month questionnaires. Participants will record details of their pessary use (insertion, removal, replacement, complications) in a diary (alongside their PFMT exercise recordings). Participants continuing pessary use after their time in the trial will receive care via their centre's usual pessary service.

An initial programme theory has been developed, proposing the pathway between intervention and outcome (Figure 1). The hypothesised mechanism of action is that successful pessary use will anatomically correct the prolapse. The anatomical correction will enable a more effective pelvic floor contraction which will lead to a greater improvement in prolapse symptoms than PFMT alone. Contextual factors suggested by previous evidence and theory to influence the pathway to outcome are included in the programme theory. Specifically, the outer circle signifies that intervention delivery, and outcomes are all influenced by context [22]. The nature of the

IRAS ID: 338183 PEPPY protocol version 3.0 26/02/2025 ISRCTN: xxxxxx Page 19 of 51

influence of contextual factors will be explored in the process evaluation. As an example, it is hypothesised that changes in symptoms due to the interventions may influence adherence differently, and the combination of the effectiveness of the contraction and the adherence to the prescribed regimen of PFMT will in turn influence outcome.

Figure 1. Proposed programme theory

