4.8 Blinding

It is not possible to blind women or treating clinical staff to group allocation, however assessment of pelvic floor muscle function and prolapse severity at 12-month follow-up will be conducted by an assessor blinded to the participant's trial group. Participants will be requested in correspondence relating to their appointment not to disclose their group allocation to the blinded assessor, and the assessor will remind them of this at the start of the examination appointment. The assessor will be asked to record whether or not they were aware of group allocation prior to the assessment.

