5.2 Supervised PFMT

The control group will receive supervised PFMT, as described above (section 5.1), without addition of a pessary. This is in line with the standard NHS patient care pathway recommended for women presenting with symptomatic prolapse which is a 16-week supervised programme of PFMT [1].

6. **OUTCOME MEASURES**

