Outcomes will be measured at baseline, 6 months and 12 months (with the exception of pelvic floor muscle and prolapse severity assessments which take place at baseline and 12 months). Pessary use will be paused 2 weeks before the 6 and 12 month time-points for women in the PFMT plus pessary group, to allow the pelvic organs to reposition without the pessary support prior questionnaires being completed and (at 12 months) clinical assessment being carried out. We will record if women do not pause pessary use prior to assessment and use this information in a sensitivity analysis.

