7.2 Measuring outcomes

Table 2 summarises what measures are assessed at baseline, 6 and 12 month time-points. Further details about outcome measures are provided above in section 6.2. The Patient Global Impression of Severity (PGI-S) (single-item participant rating of condition severity, with 4 responses from "normal" to "severe") will be included in the baseline questionnaire in place of the PGI-I [34]. Data on intervention fidelity will be gathered at each PFMT appointment by the treating clinician who will review the participant's PFMT/pessary diary and record fidelity to PFMT and pessary use (where appropriate).

Outcome data will be collected from participants mainly using participant-completed questionnaires administered via post, e-mail and telephone as required. If a questionnaire is not returned after the first request, two further requests will be made by the Trial Office. The first reminder will be by email/letter based on the participant's preference. The second reminder will be by phone, and if the participant agrees the data will be collected over the phone. Gift vouchers to the value of £10 will be sent to participants with their 12 month questionnaire.

Table 2. Overview of trial outcome measure data collection

| Data collected | Time-point | | | |
|---|--------------|--------------------------------|-------------|--|
| | Baseline | 6 months* | 12 months* | |
| Primary Outcome | | | | |
| Pelvic floor symptoms (PFDI-20) | Q | Q | Q | |
| Secondary Outcomes | | | | |
| Condition-specific quality of life (PFIQ-7) | Q | Q | Q | |
| Patient Global Impression of Improvement (PGI-I) | Q (PGI-S) | Q | Q | |
| Sexual function (ICIQ-VS Sexual Matters subscale) | Q | Q | Q | |
| Uptake of other prolapse treatment | | Q | Q | |
| Self-efficacy for treatment | Q | Q | Q | |
| Intervention adherence (PFMT + pessary) | | opointments 1-4 & uestionnaire | Q | |
| Pelvic floor muscle strength / function (MOS) | С | | C (blinded) | |
| Prolapse severity (POP-Q) | Cs | | C (blinded) | |
| Economic outcomes | | | | |
| General health-related quality of life (EQ-5D-5L) | Q | Q | Q | |
| Healthcare utilisation questionnaire | Q | Q | Q | |

^{*} women in the PFMT plus pessary group will have a pessary review appointment at 2 weeks before they receive their 6 and 12 month questionnaires at which the pessary will be removed (if they are still

IRAS ID: 338183 PEPPY protocol version 3.0 26/02/2025 ISRCTN: xxxxxx Page 22 of 51

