7.4 Follow-up

6 month follow-up

The 6 month questionnaire will be posted or emailed to participants for completion. Women using a pessary will be asked to pause pessary use 2 weeks before completion of this questionnaire. An appointment for pessary removal will be arranged if required.

12 month follow-up

The 12 month questionnaire will be posted or emailed to participants for completion. Women using a pessary will be asked to pause pessary use 2 weeks before completion of this questionnaire. An appointment for pessary removal will be arranged if required. Participants will attend a 12 month appointment for blinded assessment of pelvic floor muscle strength/function and prolapse severity.

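### The pessary pause brings pessary users a contact about 2 weeks before each outcome questionnaire, with no stated counterpart for PFMT-alone women: a probably small risk to the comparison that a common notice would reduce

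*Protocol*

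**What the plan says.** The pause is described in four places in the protocol.

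- **Section 5.1.** For self-managers: "Participants who self-manage their pessary (who can remove the pessary themselves) will be asked to remove the pessary". The others "will be asked to come to clinic to have the pessary removed 2 weeks before they receive their 6 and 12 month questionnaires".
- **Section 6.2.** "Pessary use will be paused 2 weeks before the 6 and 12 month time-points for women in the PFMT plus pessary group". The stated purpose is to let the organs reposition before symptoms are reported.
- **Section 7.2, footnote to Table 2.** "women in the PFMT plus pessary group will have a pessary review appointment at 2 weeks before they receive their 6 and 12 month questionnaires", with removal at that visit for those still using one.
- **Section 7.4.** "Women using a pessary will be asked to pause pessary use 2 weeks before completion of this questionnaire", with a removal appointment where one is needed.

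For the comparator, section 5.2 says: "The control group will receive supervised PFMT, as described above (section 5.1), without addition of a pessary". Supervised PFMT lasts 16 weeks in both arms, and nothing schedules a contact for PFMT-alone women shortly before the 6- or 12-month questionnaire. The questionnaires are posted or emailed to everyone. On non-return, section 7.2 makes no distinction by arm: "If a questionnaire is not returned after the first request, two further requests will be made by the Trial Office". All participants are invited to a blinded examination at 12 months (section 7.4).

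The primary outcome is participant-reported PFDI-20 at 12 months (section 6.1). On blinding, section 4.8 says: "It is not possible to blind women or treating clinical staff to group allocation".

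**The concern.** The pause is part of measurement rather than of treatment, and it is well motivated: section 1.1 criticises the one earlier trial of this comparison for having no washout. Its side effect is that women still using a pessary hear from or see staff about 2 weeks before a questionnaire, while PFMT-alone women have no stated contact until the questionnaire arrives.

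Two routes could carry this into the treatment comparison.

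1. **Response.** A recent contact may make a woman more likely to return the questionnaire. If so, harder-to-reach women enter the pessary-arm mean while their counterparts are missing from the other mean. The longitudinal model in section 10 assumes missingness at random, so it corrects this only as far as the covariates and the 6-month score explain it. Response at 6 months is open to the same imbalance.
2. **Reporting.** A clinic contact shortly before self-report may shift the answers of women who do respond. No missing-data method corrects that.

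**Working it through.** **Plan's own figure.** Inputs from section 9.1: difference 12, SD 40, two-sided alpha 0.05, power 90%, loss 15%.

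n per arm = 2 × (1.960 + 1.282)² × 40² / 12² = 233.5, so 234. Then 234 / 0.85 = 275.3, so 276 per arm and 552 in total. This matches the plan. With 276 × 0.85 = 234.6 analysed per arm, the standard error of the difference is 40 × √(2/234.6) = 3.69 points.

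**Response route.** Let PFMT-alone response be 85% (the plan's 15% loss), let the pessary arm gain g percentage points, and let the extra responders differ from the rest by d PFDI-20 points that the model does not explain. The pessary-arm mean then moves by

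bias = g / (85 + g) × d.

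The protocol gives neither g nor d. Nor is the whole arm exposed. Section 9.1 allows 40% fitting non-success, and section 5.1 makes use after 16 weeks optional. If a fraction f is contacted and response among them rises by h points, then g = f × h. With f = 0.60 (the plan's fitting success, used as a stand-in for use at follow-up):

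| h (assumed) | g = 0.6h | d = 10 | d = 20 | d = 30 |
|---|---|---|---|---|
| 3 | 1.8 | 0.21 | 0.41 | 0.62 |
| 5 | 3.0 | 0.34 | 0.68 | 1.02 |
| 8 | 4.8 | 0.53 | 1.07 | 1.60 |

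The central cell, 0.68, is 6% of the 12-point target (0.68/12) and 0.18 of a standard error (0.68/3.69). If only 30% still use a pessary, the same h and d give g = 1.5 and 1.5/86.5 × 20 = 0.35.

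Applying gains of 3, 5 and 8 points to the whole arm gives 3/88 × 10 = 0.34 up to 8/93 × 30 = 2.58, with 5/90 × 20 = 1.11 in the middle. The top of that range is demanding. With 60% contacted, an 8-point arm gain needs 8/0.6 = 13.3 points among them, or 98.3% response. A d of 30 is 75% of the assumed SD of 40.

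**Reporting route.** If 60% are contacted and each shifts by 2, 4 or 6.2 points (assumed; 6.2 is the lower limit of important difference in section 9.1), the arm difference moves by 1.2, 2.4 or 3.7 points. With no true effect, two-sided rejection becomes about 6%, 10% or 17%. If the shift works against the pessary arm, power at 12 points falls from 90% to about 83%, 74% or 61%. Nothing in the protocol says whether any such shift occurs, so these figures show sensitivity only.

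**Who is contacted.** Section 5.1 limits the clinic visit to women who do not self-manage. Section 7.4 arranges an appointment only where required. The Table 2 footnote places a review appointment with women in the pessary group. Section 7.4 speaks of pessary users, so it could also cover a PFMT-alone woman who takes one up. The exposed fraction is therefore not fixed by the text.

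**The case against.** The case against is substantial.

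- **Differential response is an inference.** No section says that the pause contact announces the questionnaire. Removal takes place at the centre, while the Trial Office runs the reminders, and the protocol does not say when self-managers are asked. A reader might infer that response will differ by arm; the documents show only that contact does. This stands.
- **Safeguards exist.** Reminders go only to non-responders, so an arm that responds less receives more of them, and the second is by phone with data taken on the call. That would narrow a gap. Section 10 plans pattern-mixture analyses under departures from missing at random, which address informative non-response directly. This stands as mitigation. Those analyses examine the bias rather than prevent it, and they do not touch a shift in observed scores. The sensitivity analysis in section 6.2 concerns failure to pause, not unequal contact.
- **Both arms have contact around the primary time-point.** The 12-month examination and its correspondence reach everyone. Its timing relative to the questionnaire is not fixed, so it may or may not balance the pause contact. The clear contrast is at 6 months, which is not the primary time-point but does feed the model.
- **The asymmetry follows from a justified washout in a trial that cannot be blinded.** True, and the washout should stay. It does not follow that the other arm must go without advance notice.

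**Conclusion.** The protocol ties a contact, and for some women a clinic visit, about 2 weeks before the 6- and 12-month questionnaires to women still using a pessary, in practice in the PFMT plus pessary arm. It states no matching contact for PFMT-alone women. On an open-label self-reported outcome this could produce differential response or reporting.

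Size and direction cannot be derived from the documents. Under assumed inputs that allow for partial exposure, the response route is probably about 1 point or less on PFDI-20, well inside one standard error of 3.69. The reporting route has no basis for an estimate. Reminders and pattern-mixture analyses mitigate the problem without removing it.

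A reader might infer that the primary comparison is biased, or biased by as much as 2.6 points. The documents do not support that: the figure needs the whole arm to gain 8 points of response and an unexplained difference of 30 points. This is an optional, low-cost improvement and does not affect the sample size.

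**What to change.** - In sections 7.2 and 7.4, have the Trial Office send every participant in both arms the same neutral notice, at the same time-points, that the 6- or 12-month questionnaire is coming.
- Send it early enough that any pessary removal can still be arranged by the existing 2-week point. A notice arriving exactly 2 weeks before would be too late to book a clinic removal without shortening the washout. The pause request can sit in the same notice, worded for anyone using a pessary.
- Leave the washout unchanged.
- Report response by arm at 6 and 12 months.
- Acknowledge that the removal visit remains an unequal contact. A letter equalises advance notice, not a visit.
- Reconcile section 5.1, the Table 2 footnote and section 7.4 on who attends that visit.

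The cost is two short letters or emails per participant and a few lines of protocol text, with no extra visit.

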5.2 Supervised PFMT

The control group will receive supervised PFMT, as described above (section 5.1), without addition of a pessary. This is in line with the standard NHS patient care pathway recommended for women presenting with symptomatic prolapse which is a 16-week supervised programme of PFMT [1].

6. **OUTCOME MEASURES**

6.1 Primary outcome measure

Our primary outcome measure is participant-reported symptoms of pelvic floor dysfunction measured using the Pelvic Floor Dysfunction Inventory-20 (PFDI-20) [29] at 12 months. PFDI-20 measures the severity of pelvic floor-related symptoms. It contains 20 questions about the presence of prolapse (6 items), bladder (6 items) and bowel (8 items) symptoms, and how bothersome these are, with three respective subscales (UDI-6, CRADI-8, POPDI-6). Each subscore ranges from 0-100 and the total score from 0-300: higher scores reflecting more bothersome symptoms.

6.2 Secondary outcome measures

Secondary outcomes include participant-reported pelvic floor dysfunction-related quality of life (QoL) measured using the Pelvic Floor Impact Questionnaire-7 (PFIQ-7) [23]. The PFIQ-7 was developed and validated in parallel with the PFDI-20 and includes questions on the effect of bladder (7 items), bowel (7 items) and prolapse (7 items) symptoms on activities, relationships and feelings. There are three subscales (UIQ-7, CRAIQ-7, POPIQ-7), with each sub-score ranging from 0-100, and the total score ranging from 0-300: higher scores reflect more impact on quality of life.

Other participant-reported secondary outcomes are general health-related QoL (EQ-5D-5L) (two-part instrument: five items on mobility, self-care, usual activities, pain/discomfort and anxiety/depression, plus the EQ-5D Visual Analogue Scale) [24]; Patient Global Impression of Improvement (PGI-I) (single-item participant rating of change in a condition since having treatment, validated for prolapse, with 7 responses from "very much better" to "very much

PEPPY protocol version 3.0 26/02/2025 **ISRCTN: xxxxxx** Page 20 of 51 worse") [25]; the ICIQ Vaginal Symptoms (ICIQ-VS) Sexual Matters subscale, with 4 items and score from 0 to 58, higher scores indicating worse sexual function [26]; uptake of other prolapse treatment (including surgery); self-efficacy for PFMT (Pelvic Floor Muscle Exercise Self-Efficacy Scale) [27]; and adherence to trial interventions (exercise/pessary use and experience diary).

An economic outcome, Quality Adjusted Life Years (QALYs), will be calculated from EQ-5D-5L data using the recommended tariff values [28].

Two clinical secondary outcomes are pelvic floor muscle strength and function (Modified Oxford Scale (MOS), 0 "no contraction" to 5 "strong (with lift) contraction", assessed via digital palpation) [29]; and prolapse severity (Pelvic Organ Prolapse Quantification (POP-Q) method, Stage I-IV) [20]. From our experience, use of the POP-Q system is challenging to implement in trials across many centres and different health professional groupings, therefore an experienced gynaecologist will be identified to undertake the POP-Qs at each centre.

Outcomes will be measured at baseline, 6 months and 12 months (with the exception of pelvic floor muscle and prolapse severity assessments which take place at baseline and 12 months). Pessary use will be paused 2 weeks before the 6 and 12 month time-points for women in the PFMT plus pessary group, to allow the pelvic organs to reposition without the pessary support prior questionnaires being completed and (at 12 months) clinical assessment being carried out. We will record if women do not pause pessary use prior to assessment and use this information in a sensitivity analysis.

6.3 Long term outcomes

To facilitate the possibility of assessment of long term outcomes we will consent (Consent Form 01) women to long-term follow-up via routine health records and follow-up questionnaires.

7. DATA COLLECTION AND PROCESSING

7.1 Pilot study data collection on recruitment

The Trial Office will record the number of centres open to recruitment and number of participants recruited per centre per week. Screening logs completed by centres will be reviewed monthly during the internal pilot phase to assess the numbers of participants invited and recruited to the trial. Recruitment issues in centres will be identified early and solutions put in place to rapidly resolve them.

Audio-recordings will be made of a sample of recruitment discussions to support trial recruitment methods [30-32]. Potential participants will receive a letter (Letter 02), 'recruitment study PIL' (PIL 02) and consent form/link to e-consent form (Consent Form 02) either in clinic or, in most cases, by post after receipt of their expression of interest form. On that Expression of Interest form, potential participants can indicate if they are willing to hear more about the recording of the recruitment discussion, only those who tick 'yes' will be sent an information pack. Potential participants can return a paper copy of the consent in a stamped addressed envelope or complete e-consent. The link for e-consent is embedded within the invitation Letter 02 and within the PIL. The link will connect to a GCU secured REDCAP form. Once completed by the participant it will be checked by a member of the PEPPY research team who will countersign it and return a copy to the participant.

On receipt of consent and with consent from the recruiter (Consent 05), approximately 10 recruitment conversations will be audio-recorded using small, unobtrusive digital recorders. At least one recording will be from each of the 5 pilot centres. If more than one person is undertaking recruitment at a centre, recruitment will sample for diversity in professional background of recruiter. Sampling will also target variation in women's characteristics such as ethnicity.

Approximately 3-5 interviews with participants from each trial group will be undertaken as part of the pilot to explore women's views of recruitment and of the trial generally. Approximately 5

IRAS ID: 338183 PEPPY protocol version 3.0 26/02/2025 ISRCTN: xxxxxx Page 21 of 51

recruiters (1 per pilot centre) will be interviewed at the end of the pilot study to explore their views of recruitment and of the trial generally.

Audio-recordings of recruitment sessions and extracts of data from interviews in the pilot phase that are specific to recruitment will be transcribed verbatim (see Section 12). Analysis will follow a Framework Approach [33] that will focus on actions that can be taken to support recruitment. Analysis and data extracts will be presented to PPI and other research team members for discussion about guidance for centres to support ongoing recruitment. Pilot study audio-recordings of appointments between participants and treating clinicians will be transcribed verbatim. Data will be analysed using the developed analytic framework (see Section 12). For more detail on the processes of data collection and analysis of audio-recordings and interviews please see process evaluation Section 12.

